Following consent, patients completed a baseline survey either online or through a paper survey mailed to them (see Measures) and self-collected and returned a dried blood spot (DBS) kit to assess HIV viral load (see HIV Viral Load Testing). Following baseline survey and DBS completion, participants were randomized to one of 16 conditions (see Study Design and Randomization) and invited to participate in 0, 1, 2, 3, or 4 of the interventions (see Interventions). Following intervention delivery and at least 90

days after baseline survey completion, participants were invited to complete a follow-up survey and DBS kit.

This research was approved by the Medical College of Wisconsin Institutional Review Board (protocol #PRO00037672), and the trial was registered at ClinicalTrials.gov (protocol #NCT04549259).

Measures

Unless otherwise detailed, measures were completed at both baseline and follow-up.

Demographics

Participants reported their state of residence, age, gender identity, race and ethnicity, sexual orientation, education, annual income, work status, insurance type, and year of HIV diagnosis.

Participants reported whether or not they currently had each of 16 comorbid health conditions (e.g., cancer, diabetes, heart disease, etc.). We coded the mode of data collection (online or on paper).

Primary Outcomes

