Health-related quality of life. Quality of life (QOL) was assessed with 31 items from the WHOQOL-HIV BREF³ (e.g., “How would you rate your quality of life?”). Domains assessed include physical health; psychological health; level of independence; social relationships; environmental health; and personal beliefs. Additionally, two individual items focus on overall quality of life and general health. Items focus on the past 2 weeks, and all items are responded to using 5-point Likert scales. Domain scores were created as described by the WHO, with scores within each domain ranging from 4 to 20.⁴ We also created a composite quality of life score by equally weighting the 6 domains, overall quality of life item, and general health item. This composite score is in line with research supporting a single quality of life factor³; additionally, there was good reliability ($\alpha = .87\text{-.90}$) for these 8 indicators. The composite score was rescaled such that overall scores ranged from 0 to 100, with higher scores indicating better health-related QOL. We focus here on overall QOL and on the personal beliefs subscale (e.g., “To what extent do you feel your life to be meaningful?”).

Depressive symptoms. Depressive symptoms during the past 2 weeks were assessed with the 9 items from the Patient Health Questionnaire-9 (PHQ-9)⁵ ($\alpha = .87\text{-.90}$). Participants indicated how often

they had experienced different depressive symptoms (e.g., “Feeling down, depressed, or hopeless”). Responses ranged from not at all (0) to nearly every day (3). Items were summed; higher scores indicated more depressive symptoms.

ART adherence. Adherence to HIV antiretroviral medications in the past 30 days was assessed with the 3 items from the Wilson adherence scale⁶ (e.g. “In the last 30 days, on how many days did you miss at least one dose of any of your HIV medication(s)?”, $\alpha = .71\text{-.79}$). This scale was scored in line with Wilson et al.,⁶ with scores ranging from 0 to 100 and higher scores indicating better adherence. Due to significant skew in this outcome, we created a binary variable indicating perfect adherence to HIV medications (0 = imperfect adherence, 1 = perfect adherence).

Mediating Mechanisms

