This pilot was designed to test the feasibility and acceptability of both the interventions and of a multiphase optimization strategy (MOST) design. MOST involves testing the impact of multiple interventions or intervention components simultaneously using a factorial design.¹² Therefore, using the REDCap randomization module, participants were randomly assigned to 1 of 16 conditions in a 2 (social support groups) x 2 (stigma reduction groups) x 2 (SBCM) x 2 (technology detailing) between-participants factorial design. Based on condition, participants were invited to participate in 0, 1, 2, 3 or 4 of the interventions. Information on the 16 conditions is provided in Table 1. To balance the number of participants in groups over time, randomization occurred in blocks of 32. Neither participants nor study staff were blinded to participant randomization.

Interventions

Prior work of our team and others identified factors that may affect health-related quality of life, engagement in medical care, medication adherence, and viral suppression. We chose interventions that aimed to increase social support, decrease HIV-related stigma, overcome participants' structural barriers to care, and increase technology use to engage in healthcare for this study. We aimed to identify evidence-based interventions—that could potentially be delivered remotely—to target each domain. Prior to enrolling participants, we conducted interviews with staff members at our community partner agencies to discuss our proposed interventions and receive input on how best to adapt their implementation for our target population. Following this input, each intervention was fully manualized and staff members were trained on the interventions they delivered.

Participants were randomly assigned to participate in zero to four of the interventions. All participants also received written information on healthy aging with HIV. Receipt of this information served as the control condition for those not assigned to any intervention group.

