To test preliminary impact, we fit linear and generalized linear mixed models using the R package *lme4*. For continuous outcomes (QOL, depressive symptoms, social support, loneliness, internalized stigma, QOL personal beliefs, and eHealth literacy), we fit linear mixed models with the *lmer* function, and for categorical outcomes (medication adherence, DBS VL, and service utilization), we fit generalized mixed-effect logistic regression models with the *glmer* function and a logit link. Models included a random effect for participant and utilized all available data, including baseline data from participants missing follow-up data. Predictors (fixed effects) included time (baseline vs. follow-up), random assignment to each of the 4 interventions, and interactions between assignment to the 4 interventions and time. We adjusted for mode of survey completion, which differed for those with and without follow-up data as well as for those assigned vs. not assigned to the stigma reduction groups. Interaction terms were of primary interest, with significant interactions indicating differential changes in outcomes over time for those randomly assigned vs. not randomly assigned to different interventions. Due to the small sample size, we did not test interactions between different interventions. For continuous outcomes, we calculated Cohen's *d* as a measure of effect size using the R function *lme.dscore* in the *EMAtools* package, which calculates Cohen's *d* from the mixed model results. For categorical outcomes, we report odds ratios as a measure of effect size.

Given that our factorial design resulted in many "control" participants who were assigned to alternative interventions, for this pilot we also report on changes over time in outcomes for participants randomly assigned to each intervention. These changes were once again tested with mixed models that contained only participants assigned to each intervention. Here, time was the predictor of interest, and we again controlled for mode of survey administration.

All tests performed were 2-sided. Given that the study was a pilot, we used $\alpha = .25$ as a significance level cutoff and focus primarily on patterns in the data and effect sizes.

Table 1

Random Assignments in the Full Factorial Multiphase Optimization Strategy (MOST) Design

Condition #	Social Support	Stigma Reduction	SBCM	Tech Detailing	HIV Info	N Assigned
1	OFF	OFF	OFF	OFF	ON	4
2	OFF	OFF	OFF	ON	ON	4
3	OFF	OFF	ON	OFF	ON	4
4	OFF	OFF	ON	ON	ON	4

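### Baseline precedes randomisation, yet the continuous-outcome models estimate a baseline difference for each intervention: valid and unbiased, but usually less precise than baseline adjustment

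*Combined protocol and SAP*

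**What the plan says.** Participants and Procedures gives the order of events: "Following baseline survey and DBS completion, participants were randomized to one of 16 conditions". Data Analysis lists the fixed effects: "Predictors (fixed effects) included time (baseline vs. follow-up), random assignment to each of the 4 interventions", plus assignment-by-time interactions and survey mode. The target is stated there too: "Interaction terms were of primary interest, with significant interactions indicating differential changes in outcomes over time". The models have a random effect for participant and "utilized all available data, including baseline data from participants missing follow-up data". Survey mode was added as a covariate, "which differed for those with and without follow-up data as well as for those assigned vs. not assigned to the stigma reduction groups". Seven outcomes are treated as continuous, and Cohen's d is derived from the mixed-model output. No model in the section takes baseline as a covariate or sets baseline means equal across assignments. On purpose, Study Design and Randomization says: "This pilot was designed to test the feasibility and acceptability of both the interventions".

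**The concern.** With baseline as the reference time, each assignment main effect is the baseline difference between those assigned and not assigned to that intervention. Randomisation came later, so these four parameters are zero in expectation and anything observed is chance. Estimating them freely makes each assignment-by-time term a difference in change scores. The most precise weight for the baseline difference is the slope of follow-up on baseline, which equals the correlation when the two SDs are equal. When that slope is below 1, a weight of 1 over-corrects for chance imbalance and adds variance.

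What is at stake is precision. The plan says it will concentrate on patterns and effect sizes, and each contrast compares about 30 participants with 31. Baseline data already in hand could make those effect sizes somewhat less noisy.

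**Working it through.** **Inputs from the documents.** Table 1 has 13 cells of 4 and 3 cells of 3: 13 × 4 + 3 × 3 = 61. The numbers assigned are 30 (social support), 29 (stigma reduction), 31 (SBCM) and 31 (technology detailing). Seven continuous outcomes × 4 interventions = 28 contrasts. The plan gives no power, precision or information figure to reproduce.

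**Assumed, because the documents do not give them.** Correlation ρ between baseline and follow-up: 0.4, 0.6, 0.8. Share with follow-up f: 0.8, with other values shown. Ratio k of follow-up SD to baseline SD: 1, then 0.8 and 1.2.

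**Large-sample formula.** With baseline SD 1 and leaving out the common factor in N:

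- Baseline-adjusted: k²(1−ρ²)/f
- Planned: k²(1−ρ²)/f + (1−ρk)² + (ρk−b)²(1/f−1), where b = 2ρk/(1+k²) is approximately the slope implied by a random-intercept model with equal variances.

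For k = 1, b = ρ and the last term vanishes. The ratio of adjusted to planned variance is then 1/[1 + f(1−ρ)/(1+ρ)]. At f = 0.8:

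- ρ = 0.4: 1/(1 + 0.8 × 0.6/1.4) = 0.745
- ρ = 0.6: 1/(1 + 0.8 × 0.4/1.6) = 0.833
- ρ = 0.8: 1/(1 + 0.8 × 0.2/1.8) = 0.918

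Other follow-up shares, for ρ 0.4 to 0.8: 0.70 to 0.90 with none missing, 0.722 to 0.909 with 10% missing, 0.769 to 0.928 with 30% missing.

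**At N = 61 with the covariance estimated.** The Table 1 layout was simulated with survey mode in every model and REML for the mixed models: 2,500 trials × 4 contrasts per setting. About 20% of follow-up was missing (follow-up 90% in one mode and 70% in the other, a 50% mode share and a 0.3 SD mode effect, all assumed). Variance ratios to the planned model, equal SDs:

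| | ρ = 0.4 | ρ = 0.6 | ρ = 0.8 |
|---|---|---|---|
| Large-sample formula | 0.745 | 0.833 | 0.918 |
| Common baseline, unstructured covariance | 0.776 | 0.873 | 0.939 |
| ANCOVA, completers | 0.789 | 0.893 | 0.959 |

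In a separate simulation that kept the equal-variance structure and changed only the baseline constraint, the reductions were about 24%, 15% and 7 to 8%. The gain therefore comes from the constraint and not from the change of covariance.

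**Unequal SDs, 20% missing.** For k = 0.8 and ρ = 0.4 the formula gives 0.672/(0.672 + 0.462 + 0.001) = 0.592. For k = 1.2 and ρ = 0.8 it gives 0.648/(0.648 + 0.002 + 0.007) = 0.986. Over ρ 0.4 to 0.8:

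| | k = 0.8 | k = 1.2 |
|---|---|---|
| Large-sample formula | 0.592 to 0.682 | 0.847 to 0.986 |
| Common baseline, N = 61 | 0.618 to 0.694 | 0.876 to 1.012 |
| ANCOVA, N = 61 | 0.62 to 0.71 | 0.90 to 1.04 |

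**Chance imbalance.** The SD of a baseline difference is √(1/30 + 1/31) = 0.256 baseline SDs (√(1/29 + 1/32) = 0.256 for stigma reduction). About 28 × 0.317 = 8.9 of the 28 contrasts should exceed it. With equal SDs, a difference of that size separates the planned estimate from the optimally adjusted one by (1−ρ) × 0.256 = 0.15, 0.10 and 0.05 SD at ρ = 0.4, 0.6 and 0.8.

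**Error rates.** At nominal 0.25, over 18 simulated settings (Monte Carlo error about 0.005), rejection under no effect was 0.238 to 0.267 for the planned model, 0.247 to 0.272 for the common-baseline model and 0.240 to 0.261 for ANCOVA.

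**The case against.** The strongest reply is that nothing here is wrong. A group-by-time mixed model is a standard choice, the stated target is differential change, and the plan pairs it with within-intervention change over time. The trial is a feasibility and acceptability pilot, and no decision rule in the documents depends on these standard errors.

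Most of this stands and is why the priority is low. The point about change does not remove the concern. With baseline measured before randomisation, the expected difference in change equals the expected difference at follow-up, so a baseline-adjusted model estimates the same contrast. The within-intervention summaries are not affected.

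A second reply is that any figure depends on assumptions. That also stands: 20% missing is not a trial fact, since the documents show only that some follow-up was missing. The equal-SD figures are one slice of a range that includes no gain.

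A third is that a further post hoc analysis of 28 contrasts at a .25 cutoff invites selective reporting. That is a fair cost. It is met by using one model, reporting every contrast and keeping the planned results in view.

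A reader might infer that the planned tests are biased or have inflated error. The documents do not support this: under randomisation the planned contrast is unbiased, and its simulated rejection rate was close to nominal. Nor do they support a claim about the binary outcomes. Adherence was dichotomised for skew ("Due to significant skew in this outcome, we created a binary variable indicating perfect adherence to HIV medications"), its proportion is not given, and no gain is claimed there.

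**Conclusion.** The concern holds as a matter of efficiency. The continuous-outcome models spend four parameters on baseline differences that randomisation makes zero in expectation, and usually lose precision by doing so.

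Assuming ρ of 0.4 to 0.8, equal SDs and 20% missing follow-up, baseline adjustment reduces the variance of each contrast by about 25% at ρ = 0.4 (21 to 24% in the simulations at N = 61). At ρ = 0.8 the reduction is 4 to 8%, depending on the model. If follow-up SDs are 0.8 times baseline, the reduction can reach about 38%. If they are 1.2 times baseline and ρ is 0.8, there is no gain or a slight loss. The trial's own data would settle where each outcome lies. This is a cheap improvement that the investigators could make, not an error that they must correct.

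**What to change.** For the seven continuous outcomes, estimate the four intervention effects with one baseline-adjusted model, chosen before it is fitted:

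- **Common-baseline longitudinal model:** time, four assignment-by-time terms and survey mode, no assignment main effects, an unstructured 2×2 covariance, REML and small-sample degrees of freedom. It keeps participants with baseline data only.
- **ANCOVA (simpler):** follow-up on baseline, the four assignments and survey mode.

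Do not simply delete the main effects from the existing *lmer* model. With its equal-variance structure, simulated reported variances were 15 to 21% too small when the follow-up SD was 1.2 times baseline and 22 to 26% too large when it was 0.8 times.

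Report the adjusted differences for all 28 contrasts, divided by the baseline SD, beside the planned results. The document is written in the past tense, so label them as added post hoc. Leave the binary-outcome models unchanged.

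The cost is a modest refit with no new data. The common-baseline test can be slightly liberal, ANCOVA loses baseline-only participants, and a gain is not guaranteed.

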We also assessed several factors we viewed as potential mediating mechanisms. Theorized mechanisms for the social support and stigma reduction groups were social support, loneliness, and internalized stigma. Theorized mechanisms for strengths-based case management (SBCM) were accessing needed services and the personal beliefs subscale of the quality of life measure (discussed above). Finally, a theorized mechanism for the technology detailing intervention was eHealth literacy.

Social support. Social support was assessed with 19 items from the MOS Social Support Scale⁷ ($\alpha = .98$). Participants indicated how often different kinds of support were available to them (e.g., “Someone who understands your problems”) on a scale from none of the time (1) to all of the time (5). Items were averaged; higher scores indicated more support.

Loneliness. Loneliness was assessed with 5 items from the Loneliness survey from the NIH Toolbox ($\alpha = .95\text{-.96}$).⁸ Participants indicated how often during the past month they had felt various ways (e.g., “I feel isolated from others.”) on a scale from never (1) to always (5). Items were averaged; higher scores indicated greater loneliness.

Internalized stigma. Internalized stigma was assessed with 6 items from the internalized stigma subscale of the HIV Stigma Mechanisms scale (e.g., “I feel ashamed of having HIV,” $\alpha = .95$).⁹

Responses were on a scale from *strongly disagree* (1) to *strongly agree* (5). Items were averaged; higher scores indicated more internalized stigma.

Accessing needed services. Participants reported which of 12 HIV-related social and medical services they had needed during the previous 12 months (e.g., mental health counseling, help finding meals and food, transportation, etc.).¹⁰ For those services they reported needing, participants indicated whether or not they had been able to obtain that service. A composite variable was created indicating whether participants had obtained at least one needed service (0 = no, 1 = yes).

eHealth literacy. eHealth literacy was assessed with 8 items from the eHealth Literacy Scale (e.g., “I know what health resources are available on the Internet,” $\alpha = .92\text{-.94}$).¹¹ Responses were on a scale from *strongly disagree* (1) to *strongly agree* (5). Items were averaged; higher scores indicated greater literacy.

Feasibility and Acceptability

These items were included only in the follow-up assessment.

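### Within-arm before/after tests cannot be credited to one component, and the reason given for adding them (controls received other interventions) is not a flaw in the factorial contrast

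*Combined protocol and SAP*

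**What the plan says.** The trial is a full factorial: "participants were randomly assigned to 1 of 16 conditions in a 2 (social support groups) x 2 (stigma reduction groups", crossed with strengths-based case management (SBCM) and technology detailing. The main mixed model has time, the four assignments and the four assignment-by-time interactions, adjusted for survey mode. The Data Analysis section ranks these clearly: "Interaction terms were of primary interest, with significant interactions indicating differential changes in outcomes over time". Interactions among components are left out: "Due to the small sample size, we did not test interactions between different interventions".

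The same section then adds a second analysis. Its only stated reason is that the design left many controls as "participants who were assigned to alternative interventions, for this pilot we also report on changes over time in outcomes" for those assigned to each intervention. On method it says: "These changes were once again tested with mixed models that contained only participants assigned to each intervention". On predictors: "Here, time was the predictor of interest, and we again controlled for mode of survey administration". It names no term for the other three assignments, no comparison group and no caveat on attribution. The two-sided .25 cutoff is stated for all tests, so it applies here too.

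Two other statements bear on the interpretation. Under Interventions: "All participants also received written information on healthy aging with HIV". Under Mediating Mechanisms: "Theorized mechanisms for the social support and stigma reduction groups were social support, loneliness, and internalized stigma".

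**The concern.** The rationale treats other interventions among the controls as a weakness of the ON-versus-OFF comparison that a before/after test can make up for. In a factorial design, the participants assigned to a component carry the same other interventions as its controls, so the comparison cancels them. Restricting the analysis to assigned participants leaves the co-interventions in and removes the randomised comparison.

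What is at stake is what the pilot can say about each component. A significant within-arm change could come from a co-assigned component, from the written information everyone received, or from ordinary change over time. Under worsening drift, an inert component would look harmful. The problem is concrete for the plan's own mechanism outcomes, because the social support and stigma groups share the same three theorized mechanisms and overlap heavily in membership.

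**Working it through.** The plan states no effect size, SD, correlation or dropout rate, so there is no figure of its own to reproduce. Steps 1 and 2 use only Table 1 and the model description. Step 3 rests on labelled assumptions.

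**Step 1. Are the other interventions balanced between ON and OFF?** The Table 1 cells are 4,4,4,4,4,4,3,4,4,4,4,4,3,3,4,4, which sum to 61.

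| Component | ON / OFF | At least one other, ON vs OFF | Mean number of others, ON vs OFF | Component alone |
|---|---|---|---|---|
| Social support | 30 / 31 | 26/30 vs 27/31 | 1.50 vs 1.48 | 4 |
| Stigma reduction | 29 / 32 | 25/29 vs 28/32 | 1.52 vs 1.50 | 4 |
| SBCM | 31 / 30 | 27/31 vs 26/30 | 1.52 vs 1.43 | 4 |
| Technology | 31 / 30 | 27/31 vs 26/30 | 1.48 vs 1.47 | 4 |

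The largest gap in any single co-assignment is SBCM among social support ON (16/30 = 53.3%) versus OFF (15/31 = 48.4%), about 5 percentage points. The largest correlation between any two factors is 0.049. If every component had an effect of 0.3 SD, even an unadjusted ON-minus-OFF difference would be off by at most 0.025 SD. The planned model, with all four assignment-by-time terms, removes that too under additivity.

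**Step 2. What does the within-arm time coefficient estimate?** With additive effects b on change, common change over time T, and complete data, its expectation in arm j is

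T + b_j + Σ p_jk · b_k (sum over k ≠ j),

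where p_jk is the share of arm j also assigned component k. For the stigma arm the shares are 14/29 (social support), 15/29 (SBCM) and 15/29 (technology), which sum to 44/29 = 1.517. Across all arms p_jk runs from 14/30 = 0.47 to 16/30 = 0.53. T includes any effect of the written information.

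The overlap of social support and stigma comes from conditions 13 to 16: 3 + 3 + 4 + 4 = 14, which is 14 of 29 stigma participants and 14 of 30 social support participants. Within-arm change in social support, loneliness or internalized stigma therefore cannot be assigned to either group intervention.

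**Step 3. How often would an inert component show a significant change?** Take the stigma component as inert, n = 29, with a continuous outcome and complete data. Outcome SD is 1 and the baseline/follow-up correlation r is assumed to be 0.6 (range 0.4 to 0.8). The SD of change is √(2(1 − r)) = √0.8 = 0.894. The noncentrality is (expected shift / 0.894) × √29, tested two-sided at .25 on 28 df (critical t = 1.175).

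Example: with the other three components at 0.2 SD each, the shift is 0.2 × 44/29 = 0.303, the noncentrality is 0.303/0.894 × 5.385 = 1.83, and the rejection probability is 74%.

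| Assumed truth | Within-arm significant (r = 0.4 to 0.8) |
|---|---|
| Nothing works, no drift | 25% (nominal) |
| Only social support works, 0.2 SD | 33% (30–39%) |
| Only social support works, 0.3 SD | 41% (36–54%) |
| Only social support works, 0.5 SD | 62% (52–81%) |
| Other three at 0.1 SD each | 42% (37–56%) |
| Other three at 0.2 SD each | 74% (63–92%) |
| Other three at 0.3 SD each | 94% (86 to over 99%) |
| Drift +0.2 SD, nothing works | 53% (45–71%), almost all favourable |
| Drift −0.2 SD, nothing works | 53% (45–71%), about 1% favourable |

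On the Table 1 allocation, the factorial contrast for the inert component rejected in 24–27% of simulated trials in every scenario simulated: the null, social support only at 0.2 SD, the three-component cases and drift. If 23 of 29 were followed up (assumed), the three-component figures become 39%, 68% and 90%, and drift of +0.2 SD gives 48%. Binary outcomes, the survey-mode covariate and informative dropout were not modelled.

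**The case against.** The strongest reply is that the plan never calls the factorial contrast biased. It ranks the interaction terms first, presents the within-arm changes as an addition for a pilot, and does not credit those changes to a single component. The harm therefore needs a later misreading. All of that is true and limits the seriousness of the point. But the changes are tested rather than only described, and the mixed controls are the only reason given. A reader told that the controls are contaminated will naturally look to the analysis without controls.

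A second reply is that the OFF group is not an information-only group; only condition 1 (n = 4) is. If components interact, the contrast is an average over the mix of the others. For instance, with all main effects at 0.30 SD and a −0.3 SD interaction between social support and stigma reduction, the social support term falls to about 0.16 SD. This stands as a limit on what the contrast means. It does not rescue the within-arm test, whose participants carry the same mix.

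Third, the within-arm null is no change over time, so rejecting it under drift or working co-interventions is correct. This also stands. The percentages above are not type I error rates for that null. They are the chance that a component with no effect is reported beside a significant change. The larger ones need all three other components to affect the same outcome; the overlap that the plan itself supports for the mechanism outcomes gives 33% at 0.2 SD.

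Finally, a model-based ON change averaged over the other components targets nearly the same quantity as the within-arm coefficient (weights of 0.5 instead of 0.47 to 0.53). Agreed: what the remedy adds is the OFF change beside it and the difference as the basis for inference.

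**Conclusion.** The concern holds and should be fixed. The primary interaction tests are not affected. The balance in Table 1 and the composition of the within-arm coefficient need no assumed effect sizes. Additivity is needed for the contrast to equal each component's own effect; without it, the contrast is an average effect and the within-arm coefficient is still a mixture. The size of the problem depends on assumptions: within-arm significance for an inert component ranges from the nominal 25%, when nothing else works and nothing drifts, to over 90% when three other components each work at 0.3 SD. A significant within-arm change is therefore not evidence for that component.

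**What to change.** Withdraw the stated rationale. From the full factorial model, report for each intervention the estimated change under ON, the estimated change under OFF (both averaged over the other three) and their difference, with confidence intervals. Base every statement about a component on the difference. If within-arm change is still shown, give it descriptively beside the OFF-group change, label it as including co-assigned interventions and time, and do not use its significance at .25 as evidence for the component. Say also that the difference is an average over the other components, since interactions among them are not tested.

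The cost is wording plus contrasts from a model already fitted; no new data are needed. There will be fewer significant results to report, and the intervals will be wide. With a standard error of 0.256 × √(2(1 − r)) and a t multiplier of about 2.00 on 56 df, the 95% half-width is 2.00 × 0.256 × 0.894 = 0.46 SD at r = 0.6. It is about 0.56 SD at r = 0.4 and 0.33 SD at r = 0.8, all with complete data. That width is a fair picture of what 61 participants can show.
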